4.3.1. Endpoint Definition

4.3.1.1. All-cause Mortality at Day 28 and 60

Participants will meet the endpoint if they have died due to any cause prior to Day 28 and 60. All-cause mortality will be based on the clinical status as defined in Section 6.3.2.

4.3.1.2. Time to All-cause Mortality up to Day 60

Defined as the time (days) from dosing to death, due to any cause, up to (and including) Day 60.

4.3.1.3. Participants Alive and Free of Respiratory Failure at Day 7, 14, 42, and 60

Defined as per primary endpoint, see Section 4.2.1.

4.3.1.4. Time to Recovery from Respiratory Failure up to Day 28

Defined as the time (days) from dosing to last recovery from respiratory failure up to (and including) Day 28. Participants are in respiratory failure if they are in category 5 or above from the GlaxoSmithKline (GSK) modified ordinal scale adapted from World Health Organization (WHO, 2020) scale 2020 (Table 2).

Note: if a participant has recovered from respiratory failure but then progresses back into respiratory failure on or prior to the end of follow up (Day 28) the participant has not had their last recovery from respiratory failure.

This endpoint will use a composite approach for death such that if the intercurrent event of death occurs (on or prior to Day 28), then time will be censored at end of follow up (Day 28).

4.3.1.5. Participants Alive and Independent of Supplementary Oxygen at Day 7, 14, 28, 42, and 60

Participants are independent of supplementary oxygen if they are in category 1, 2 or 3 from the GlaxoSmithKline (GSK) modified ordinal scale adapted from World Health Organization (WHO, 2020) scale 2020 (See Table 2- Ordinal Scale). Missing data prior to study withdrawal will be derived using ventilation data as described in Section 6.3.2

Participants will meet the endpoints if they are alive and independent of supplementary oxygen at Day 7, 14, 28, 42, and 60 respectively. As participants may be discharged from investigator site, analysis windows will be used to define the endpoint as described in Section 6.3.1.

4.3.1.6. Time to Last Dependence on Supplementary Oxygen up to Day 28

Defined as the time (days) from dosing to last dependence on supplementary oxygen up to (and including) Day 28. Participants are dependent on supplementary oxygen if they are in category 4 or above from the GlaxoSmithKline (GSK) modified ordinal scale adapted from World Health Organization (WHO, 2020) scale 2020 (Table 2).

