Alternatively, if the clinical status is unknown but ventilation or oxygen status is available, then the endpoint is defined as the last day up to (and including) Day 28 where oxygen support is required.

Note: if a participant is independent of supplementary oxygen but then progresses back into dependence of supplementary oxygen on or prior to the end of follow up (Day 28) the participant has not had their last dependence on supplementary oxygen.

This endpoint will use a composite approach such that if the intercurrent event of death occurs (on or prior to Day 28), then time will be censored at end of follow up (Day 28).

4.3.1.7. Time to Final ICU Discharge up to Day 28

This is defined as the time (days) from dosing to the participants final ICU discharge up to (and including) Day 28. It will only be evaluated for participants in the ICU at baseline.

This endpoint will use a composite approach such that if the intercurrent event of death occurs (on or prior to Day 28), then time will be censored at the end of follow-up (Day 28), including those that were discharged from ICU prior to death.

4.3.1.8. Time to First Discharge from Investigator Site up to Day 60

This is defined as the time (days) from dosing to when the participant is first discharged from investigator site up to (and including) Day 60.

This endpoint will use a composite approach such that if the event has not occurred prior to the intercurrent event of death (on or prior to Day 60), then time will be censored at the end of follow-up (Day 60).

4.3.1.9. Time to First Discharge to Non-Hospitalized Residence up to Day 60

This is defined as the time (days) from dosing to when the participant is discharged to a non-hospitalized residence for the first time up to (and including) Day 60.

This endpoint will use a composite approach such that if the event has not occurred prior to the intercurrent event of death occurred (on or prior to Day 60), then time will be censored at the end of follow-up (Day 60).

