4.3.2.2. Time to Event Endpoints

The following endpoints will be analysed using time to event analyses with a follow-up to Day 60:

- Time to all-cause mortality
- Time to first discharge from investigator site
- Time to first discharge to non-hospitalized residence

The following exploratory endpoints will be analysed using time to event analyses with a follow-up to Day 28:

- Time to recovery from respiratory failure
- Time to last dependence on supplementary oxygen
- Time to final ICU discharge

For time to event endpoints where the event is a worsening participant status, participants with missing data due to study withdrawal prior to occurrence of the event will be censored at the time of study withdrawal, participants alive at the end of follow-up will be censored at the time of end of follow-up (*i.e.* Day 28/60).

For time to event endpoints where the event is an improvement participant status, participants with missing data due to study withdrawal prior to first occurrence of the event will be censored at the time of end of follow-up. The end of follow up will be the earliest of the nominal timepoint (*i.e.* Day 28/60) and their actual study day of visit. If a participant meets the endpoint at the point of withdrawal, then the participant will be assumed to have achieved the event.

The endpoint will be analysed using a Cox proportional hazards model adjusted for covariates per Section 4.1.1. Ties will be broken using Efron's method. The hazard ratio of the treatment group and corresponding confidence interval and p-value will be reported. For any endpoint where a hazard ratio above 1 indicates improvement of otilimab over placebo, the inverse hazard ratio will also be presented. For model checks refer to Section 6.2.3.

Kaplan-Meier plots will be presented by treatment group. Estimates of the median time-to-event and other relevant percentiles will be derived from the unadjusted Kaplan-Meier plots and reported in a table. If 50% of participant do not meet the event definition during the study, alternative percentiles may be produced.

These time to event endpoints may also be derived using additional follow-up times to support future sensitivity analyses.

Additionally, for time to ICU discharge, the following summaries will be produced:

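### Part 2 SAP 4.3.1.6 does not censor a survivor who never came off oxygen, and read literally it gives that participant an event at Day 28

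*SAP*

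**What the plan says.** All references are to the Part 2 SAP unless stated.

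- **Main definition (4.3.1.6).** "Defined as the time (days) from dosing to last dependence on supplementary oxygen up to (and including) Day 28". Dependence means ordinal category 4 or higher.
- **Fallback (4.3.1.6).** This applies only where the ordinal category is not known but the oxygen or ventilation record is: "then the endpoint is defined as the last day up to (and including) Day 28 where oxygen support is required".
- **Note on relapse (4.3.1.6).** For someone who comes off oxygen and needs it again, the Note says: "on or prior to the end of follow up (Day 28) the participant has not had their last dependence on supplementary oxygen".
- **Death (4.3.1.6).** "if the intercurrent event of death occurs (on or prior to Day 28), then time will be censored at end of follow up (Day 28").
- **Withdrawal (4.3.2.2).** The censoring rule for this kind of endpoint opens with "For time to event endpoints where the event is an improvement participant status, participants with missing data due to study withdrawal prior to first occurrence"; such withdrawals are censored when follow-up ends. The paragraph before it says that living participants are censored at the end of follow-up, but only for endpoints where the event is a worsening.
- **Intent (1.1.2).** The text after Table 1 describes time-to-event estimands of this kind as positive outcomes, in which death should count against the participant. Table 1 lists this endpoint as Secondary 7, summarised by a hazard ratio.
- **Multiplicity (2.1).** The endpoint is not in the testing hierarchy.

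**The concern.** Participants enter in category 5 or 6 and dependence starts at category 4, so everyone is dependent at baseline and everyone has a last dependent day. For a survivor on oxygen throughout, that day is Day 28.

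The neighbouring endpoints avoid this problem because their events are improvements in themselves: recovery from respiratory failure (4.3.1.4) and final ICU discharge (4.3.1.7). Someone who never recovers, or never leaves ICU, cannot have those events. A last day of dependence is not an improvement, so the same template needs an explicit censoring sentence here, and it has none.

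At stake is a prespecified hazard ratio with confidence interval, p-value and Kaplan-Meier percentiles. Two programmers could code the never-weaned survivor differently. If that participant is coded as an event, the contrast mixes oxygen independence with survival: a real gain in independence can be hidden, and a mortality effect can appear as an oxygen effect. The Kaplan-Meier curve would also step at Day 28.

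**Working it through.** **1. Which rule reaches which participant (4.3.1.6 and 4.3.2.2).**

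| Status at Day 28 | Rule | Result |
|---|---|---|
| Off oxygen, no relapse | Main definition | Event on last dependent day |
| Came off, back on oxygen | Note | No event |
| Died by Day 28 | Death rule | Censored at Day 28 |
| Withdrew before the event | 4.3.2.2, improvement rule | Censored at end of follow-up |
| Alive, on oxygen every day | None | Last dependent day is Day 28; no sentence censors it |

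**2. The plan's own figure.** Neither document gives an event count or power for this endpoint. The sample size is set for the primary endpoint (SAP section 5; Protocol 8.2): 45% against 60%, one-sided 2.5%, 80% power. With a mean proportion of 0.525:

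n per arm = [1.960 × √(2 × 0.525 × 0.475) + 0.842 × √(0.45 × 0.55 + 0.60 × 0.40)]² / 0.15² = (1.384 + 0.588)² / 0.0225 ≈ 172.8, so 173 per arm and 346 in total.

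Power at 173 per arm is 80.05%. The stated figure reproduces, and only the 346 is carried forward.

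**3. Event proportions by hand.** Ignoring relapse and withdrawal, the literal coding gives an event to everyone alive at Day 28, so the Day 28 event proportion equals survival. Splits are off oxygen / alive on oxygen / dead.

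- Gain in independence with equal deaths, 40/25/35 against 55/10/35. Censored coding: 40% against 55%. Literal coding: 40 + 25 = 65% against 55 + 10 = 65%.
- Mortality-only difference, 40/25/35 against 40/35/25. Censored coding: 40% against 40%. Literal coding: 65% against 40 + 35 = 75%.

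A rough check on the first censored hazard ratio is ln(1 − 0.55) / ln(1 − 0.40) = 0.799 / 0.511 = 1.56.

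**4. Simulation.** 173 per arm and 800 trials per scenario. Times for those off oxygen were drawn from the same distribution in both arms, in whole days before Day 28. The model was an unadjusted Cox model with Efron ties, tested at two-sided 5%. Deaths were censored at Day 28 throughout. Survivors on oxygen were coded once as censored at Day 28 and once as events at Day 28. Entries are geometric-mean HR (rejection rate).

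| Placebo | Otilimab | Censored coding | Literal coding |
|---|---|---|---|
| 40/25/35 | 40/25/35 | 1.00 (5%) | 1.00 (6%) |
| 40/25/35 | 55/10/35 | 1.54 (78%) | 1.13 (16%) |
| 40/25/35 | 40/35/25 | 1.00 (5%) | 1.22 (35%) |
| 40/25/35 | 40/40/20 | 1.01 (4%) | 1.35 (68%) |
| 40/25/35 | 55/20/25 | 1.55 (79%) | 1.38 (69%) |
| 50/10/40 | 60/10/30 | 1.32 (48%) | 1.31 (54%) |

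Monte Carlo error on a rejection rate is at most √(0.5 × 0.5 / 800) = 1.8 points. A repeat simulation, also with 40% independent on placebo, gave 1.53 against 1.12 for equal deaths and 1.02 against 1.22 when only mortality differed.

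**5. Are the splits plausible?** They are assumptions. Oxygen independence is categories 1 to 3, a subset of the categories 1 to 4 for which the plan assumes 45% on placebo, so 40% is compatible with that figure. The last row's 50% is above it. That row only illustrates what happens when few participants remain on oxygen.

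**The case against.** The strongest reply is that the SAP read as a whole points to censoring. Section 1.1.2 treats these endpoints as positive outcomes. The withdrawal rule in 4.3.2.2 makes sense only if the event is coming off oxygen, because on the literal reading anyone withdrawing on oxygen would already have a last dependent day. The sensitivity analysis in 4.3.3.2 extends the 28-day improvement endpoints to Day 60 partly to examine time of censoring, which presupposes that participants not improved by Day 28 are censored there. Giving an event to someone never weaned, but not to someone who relapsed, is odd enough to count against the literal reading. Further data-handling conventions sit in the Output and Programming Specification, which is not among the documents.

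All of this stands as evidence of intent. It does not supply the missing sentence, and it means that the definition as worded conflicts with what the SAP sets out to measure.

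A reader might go further and infer that every participant on oxygen at Day 28 is given an event. The documents do not support that. The Note withholds it from those who relapsed, and the sentence quoted as the fallback applies only when clinical status is unknown and yields a day, not an event indicator. A reader might also infer that staying on oxygen is scored as a success. That is too strong: even read literally, the event falls at the latest possible time, so it is favourable only relative to participants without an event by that day, chiefly deaths.

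The consequence is limited. The endpoint supports no controlled significance claim, and oxygen independence is also measured by the binary endpoint at Days 7, 14, 28, 42 and 60 (4.3.1.5) and by oxygen-free days (4.4.1.6).

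**Conclusion.** The point holds as a defect in the definition, not as proof that the analysis will be run wrongly. Section 4.3.1.6 read literally gives the continuously dependent survivor an event at Day 28, nothing in the SAP censors that participant, and this contradicts the SAP's treatment of the endpoint as an improvement.

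If it is coded as written, the hazard ratio can move from about 1.5 to about 1.1 when the drug shortens oxygen need without changing deaths. It can move from 1.0 to about 1.2 when the drug only changes mortality from 35% to 25%, and to about 1.35 at 35% to 20%. These mortality-only cases assume that every averted death becomes a survivor still on oxygen, which is the unfavourable extreme. When deaths and oxygen need improve together the gap narrows (1.55 against 1.38), and with 10% on oxygen at Day 28 in both arms it nearly closes (1.32 against 1.31).

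The sizes rest on assumed splits and an unadjusted model without relapse or withdrawal. If never-weaned survivors are censored, no distortion arises. Priority is low to moderate.

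**What to change.** In Part 2 SAP 4.3.1.6, define the event as the first day of oxygen independence that is maintained through Day 28: clinical status 1 to 3, or no oxygen by the ventilation log when clinical status is unknown. State that every participant dependent on oxygen at Day 28, whether never independent or relapsed, is censored at Day 28, as is every death by Day 28. The withdrawal rule in 4.3.2.2 can stay. Carry the same wording, with Day 60 in place of Day 28, into the extended analysis in 4.3.3.2.

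Make the change before Part 2 is unblinded. It costs a sentence or two of SAP text and a matching line in the programming specification, with no new data and no change to trial conduct.

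Part 1 SAP 5.3.1.6 has the same wording, but it should not be redefined now, because Part 1 results had been seen before Part 2 was added.

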4.3.2. Main Analytical Approach

4.3.2.1. Binary Endpoints

The binary endpoints:

- All-cause mortality at Day 28 and Day 60
- Participants alive and free of respiratory failure at Day 7, 14, 42, and 60
- Participants alive and independent of supplementary oxygen at Day 7, 14, 28, 42, and 60

Binary secondary endpoints will be analysed as per Section [4.2.2](#).

4.3.2.2. Time to Event Endpoints

The following endpoints will be analysed using time to event analyses with a follow-up to Day 60:

- Time to all-cause mortality
- Time to first discharge from investigator site
- Time to first discharge to non-hospitalized residence

The following exploratory endpoints will be analysed using time to event analyses with a follow-up to Day 28:

- Time to recovery from respiratory failure
- Time to last dependence on supplementary oxygen
- Time to final ICU discharge

For time to event endpoints where the event is a worsening participant status, participants with missing data due to study withdrawal prior to occurrence of the event will be censored at the time of study withdrawal, participants alive at the end of follow-up will be censored at the time of end of follow-up (*i.e.* Day 28/60).

For time to event endpoints where the event is an improvement participant status, participants with missing data due to study withdrawal prior to first occurrence of the event will be censored at the time of end of follow-up. The end of follow up will be the earliest of the nominal timepoint (*i.e.* Day 28/60) and their actual study day of visit. If a participant meets the endpoint at the point of withdrawal, then the participant will be assumed to have achieved the event.

The endpoint will be analysed using a Cox proportional hazards model adjusted for covariates per Section 4.1.1. Ties will be broken using Efron's method. The hazard ratio of the treatment group and corresponding confidence interval and p-value will be reported. For any endpoint where a hazard ratio above 1 indicates improvement of otilimab over placebo, the inverse hazard ratio will also be presented. For model checks refer to Section 6.2.3.

Kaplan-Meier plots will be presented by treatment group. Estimates of the median time-to-event and other relevant percentiles will be derived from the unadjusted Kaplan-Meier plots and reported in a table. If 50% of participant do not meet the event definition during the study, alternative percentiles may be produced.

These time to event endpoints may also be derived using additional follow-up times to support future sensitivity analyses.

Additionally, for time to ICU discharge, the following summaries will be produced:

- For participants who are in the ICU at any point during the trial, the duration of ICU stay will be summarised overall and separately for participants that have died and those that complete the study, it will be further split by participants ICU status (in ICU at dosing or entered ICU post-dose).

- Additionally, for all participants a count and proportion of participants with stays in the ICU of 0 days, 1-<7 days, 7-<14 days and ≥ 14 days will be produced.

For hospitalization:

- The duration of hospitalization will be summarized overall and separately for participants that have died and those that complete the study. A count and proportion of participants with hospitalization stays of 1-<7 days, 7-<14 days and ≥ 14 days will be produced.
- A separate summary of discharge location will also be provided.

4.3.3. Sensitivity Analyses

4.3.3.1. Binary Endpoints

Sensitivity analyses as per Section 4.2.3 will be performed on the binary endpoints in the hierarchy specified in Section 2.1.

4.3.3.2. Time to Event Endpoints

As a sensitivity to the proportional hazards assumption, and time of censoring, for the time to event endpoints where the event is an improvement participant status with a follow up time of 28 days, the endpoints will be calculated for an extended follow-up time up to Day 60 and analysis may be performed as per Section 4.3.2.2.

4.3.4. Supplementary Analyses

Supplementary estimands as described in Section 4.2.4 may be performed on all-cause mortality endpoints (Day 28 and Day 60).

4.3.5. Subgroup Analyses

Subgroup analyses for the endpoints listed in the testing hierarchy in Section 2.1 may be performed as per Section 4.2.5 and will use the methods described above.

4.4. Exploratory Endpoint(s) Analyses

Exploratory endpoints may be analysed at the final analysis only.

4.4.1. Definition of Endpoint(s)

4.4.1.1. Invasive Mechanical Ventilation (if not previously initiated) up to Day 28

Participants will meet the endpoint if they have had invasive mechanical ventilation initiated up to (and including) Day 4, 7, 14, 28. This will only be evaluated for participants who are not supported using invasive mechanical ventilation at baseline. This will be derived from the worst-case ventilation record as detailed in Section 6.3.2.1.

Participants who die on or prior to Day 28 without the initiation of invasive mechanical ventilation will be considered to have met the endpoint (composite estimands strategy).

4.4.1.2. Invasive Mechanical Ventilation (if not previously initiated) at Day 4, 7, 14, 28

Participants will meet the endpoint if they had invasive mechanical ventilation on the specified day. This will only be evaluated for participants who are not supported using invasive mechanical ventilation at baseline. This will be derived from the worst-case ventilation record as detailed in Section 6.3.2.1.

Participants who die on or prior to the specified day will be considered to have met the endpoint (composite estimands strategy).

4.4.1.3. Time to Invasive Mechanical Ventilation (if not previously initiated) up to Day 28

Time from dosing (days) to first use of invasive mechanical ventilation or death up to (and including) Day 28 as defined in Section 4.4.1.1. This will only be evaluated for participants who are not supported using invasive mechanical ventilation at baseline. This will be derived from the worst-case ventilation record as detailed in Section 6.3.2.1.

This endpoint will use a composite approach for death such that for participants who die on or prior to Day 28 without the initiation of invasive mechanical ventilation, the time to invasive mechanical ventilation will be set as the time of death.

4.4.1.4. Alive and Not Invasively Mechanically Ventilated

Participants will meet the endpoint if they are alive and not requiring invasive mechanical ventilation at Day 7, 14, 28, 42 and 60. This will be evaluated only for participants supported using invasive mechanical ventilation at baseline. This will be derived from the worst-case ventilation record as detailed in Section 6.3.2.1.

4.4.1.5. Time to Definitive Extubation up to Day 28

For participants supported using invasive mechanical ventilation at baseline this is defined as the time from dosing (days) to final extubation from invasive mechanical ventilation up to (and including) Day 28. This will be derived from the worst-case ventilation record as detailed in Section 6.3.2.1.

This endpoint will use a composite approach for death such that if the event intercurrent event of death (on or prior to Day 28) occurs, then time will be censored at the end of follow-up (Day 28), including those that were extubated prior to death.

4.4.1.6. Oxygen-free Days up to Day 28

A participant is considered oxygen free on a day if they are not using oxygen (Ventilation=None) as derived from the worst case ventilation record on a day as detailed in Section 6.3.2.1.

Intermittent data is expected after discharge from investigator site, therefore if participants have discontinued oxygen and have been discharged to a non-hospitalized residence, they will be considered to be oxygen-free during the intermittent timepoints.

4.4.1.7. Ventilator-free Days up to Day 28

A participant is considered ventilator-free on a day if they are not using invasive mechanical ventilation as derived from the worst case ventilation record on a day as detailed in Section 6.3.2.1.

Intermittent data is expected after discharge from investigator site, therefore if participants have discontinued ventilation and have been discharged to a non-hospitalized residence, they will be considered to be ventilation-free during the intermittent timepoints.

4.4.1.8. Admission to ICU up to Day 28

Participants will meet the endpoint if they have been admitted to the ICU at any point up to (and including) Day 28, only evaluated for participants not in ICU at time of dosing.

Participants who die prior to Day 28 without being admitted ICU will be considered to have met the endpoint (composite estimands strategy).

4.4.1.9. Change from Baseline in Inspired Oxygen (FiO₂) up to Day 28

Change from baseline in FiO₂ will be calculated, for participants up to Day 28. FiO₂ will be summarized as a fraction rather than a percentage for observed data and using a trimmed means approach as specified in the Section 4.4.2.4.

For the trimmed means, if >50% of the participants experience the intercurrent events listed below at any timepoint, then the data will be summarized up to that timepoint only.

If a participant experiences multiple intercurrent events, then the worst response status will be assumed.

If FiO₂ is not recorded but Oxygen Flow Rate is, the FiO₂ will be calculated.

Intercurrent event	Response Status
Death	Non-responder
Discharge from investigator site to advanced facilitated care	Non-responder
Discharge from Investigator Site for any other reason other than advanced facilitated care	Responder
Independence from supplementary oxygen and missing FiO ₂	Responder

